Appendix 11: Schedule of Assessments

	Induction Phase					
	Visit 1	Visit 2	Visit 3	Visit 4	Visit 5	Visit 6 ^a
	Screening ≤28 days prior to Day 1	Baseline Day 1	Day 8 ^b (± 3 d)	Day 29 (± 3 d)	EOT/ET Day 57 (± 3 d)	Follow-up Day 71 (± 7 d)
Informed consent	X					
Inclusion/exclusion	X	P				
Demographics	X					
Medical history	X	P				
Concomitant medication				X		
Subject diary completion			X			
Study drug						
Randomisation		X				
Study drug administration				X		
Compliance review			X	X	X	
Safety						
Follicle-stimulating hormone ^c	X					
Pregnancy test ^d	X	P		X	X	
Viral serology	X ^e					
Clostridium difficile test	X					
Chemistry, haematology, coagulation, and urinalysis	X	P		X	X	X
Vital signs	X	P		X	X	X
12-lead ECGs	X	P		X	X	X
Physical examination	X			X	X	X
Adverse event monitoring				X		
Endoscopic and clinical assessments						
UCEIS	X				X	
Total Mayo score ^f	X				X	
Partial Mayo score ^{f,g}	X	P		X	X	
Modified Mayo score ^{f,h}	X				X	
Health-related quality of life						
IBD questionnaire		P		X	X	
Biomarkers						
C-reactive protein	X	P		X	X	
Faecal calprotectin	X	P		X	X	
Endoscopy/biopsy						
Endoscopy	X ⁱ				X ^j	
Histopathology	X				X	
Tissue concentration					X	

Abbreviations: d = days; ECG = electrocardiogram; EOT = end of treatment; ET = early termination; IBD = inflammatory bowel disease; P = predose; UCEIS = Ulcerative Colitis Endoscopic Index of Severity.

a Only for subjects who do not agree to participate in the extension phase.

b Telephone visit; however, at the discretion of the investigator, subjects may be requested to attend the study site.

c Postmenopausal females only.

d Females of childbearing potential only. A serum pregnancy test will be performed at screening and urine pregnancy tests performed at all other timepoints.

e At a minimum comprises HBV (includes HBV surface antigen, HBV surface antibody, and HBV core antibody), antibodies to hepatitis C virus, and human immunodeficiency virus.

f Mayo scores collected from 1 week prior to each visit (including endoscopy visit).

g Rectal bleeding, stool frequency, and Physician's global assessment.

h Rectal bleeding, stool frequency, and findings on endoscopy.

i Conducted within 7 days of Day 1.

j Endoscopy will be performed ≤7 days prior to the Day 57 visit or on the same day as the other Day 57 procedures/assessments.

	Extension Phase		
	Visit 7	Visit 8	Visit 9
			EOS/ET visit
	Day 71 (\pm 3 d) ^a	Day 85 (\pm 3 d)	Day 112 (\pm 3 d)
Concomitant medication		X	
Subject diary completion		X	
Study drug			
Study drug administration		X	
Compliance review	X	X	X
Safety			
Urine pregnancy test ^b		X	X
Chemistry, haematology, coagulation, and urinalysis		X	X
Vital signs		X	X
12-lead ECGs		X	X
Physical examination		X	X
Adverse event monitoring		X	
Endoscopic and clinical assessments			
UCEIS			X ^d
Total Mayo score ^c			X ^d
Partial Mayo score ^{c,e}		X	X
Modified Mayo score ^{c,f}			X ^d
Health-related quality of life			
IBD questionnaire		X	X
Biomarkers			
C-reactive protein		X	X
Faecal calprotectin		X	X
Endoscopy/biopsy			
Endoscopy			X ^g
Histopathology			X ^d

Abbreviations: d = days; ECG = electrocardiogram; EOS = end of study; ET = early termination; IBD = inflammatory bowel disease; UCEIS = Ulcerative Colitis Endoscopic Index of Severity.

a Telephone visit; however, at the discretion of the investigator, subjects may be requested to attend the study site for safety assessments.

b Females only.

c Mayo scores collected from 1 week prior to each visit (including endoscopy visit).

d If endoscopy is performed.

e Rectal bleeding, stool frequency, and Physician's global assessment.

f Rectal bleeding, stool frequency, and findings on endoscopy.

g Endoscopy performed at the discretion of the investigator. If an endoscopy is performed, it should be performed ≤ 7 days prior to the EOS/ET visit or on the same day as the other EOS/ET procedures/assessments.

Appendix 12: Summary of Changes

The following changes were implemented in Protocol Version 2:

- It was clarified that the Mayo endoscopic subscore will be assessed by both a local and qualified central reader. Locally read Mayo endoscopic subscores will be used to determine the subject's eligibility, clinical remission status, and treatment to be assigned in the extension phase. Centrally read Mayo endoscopic subscores will be used to evaluate the objectives of the study.
- Measurements of the tissue concentration of BBT-401-1S at screening were removed.
- The time window for the Day 57 endoscopy was updated.
- The time windows for visits in the extension phase were updated.
- The fasting requirements were removed.
- It was clarified that stool frequency and rectal bleeding will be documented daily by the subject.
- The unit of glomerular filtration rate was corrected.

The following changes were implemented in Protocol Version 3:

- Protocol Version 2 incorrectly stated that locally read Mayo endoscopic subscores would be used to determine the subject's eligibility. This was corrected to state that centrally read Mayo endoscopic subscores will be used to evaluate the objectives of the study.

The following changes were implemented in Protocol Version 4:

- Clarified that subjects who test positive for *Clostridium difficile* at screening will be excluded.
- Added that clinical laboratory evaluations, including liver function tests, may be repeated once, at the discretion of the investigator (or designee), to determine eligibility.
- Added that subjects may be rescreened once, at the discretion of the investigator (or designee), providing that the reason for screen failure was not due to a safety concern or non-eligibility related to clinical laboratory evaluations.
- Updated that the study treatments will be provided in bottles.
- Added locations from which biopsies will be collected.
- Added that the total Mayo score measured at screening will be used as baseline.
- Clarified that subscores of physician's global assessment component of the Mayo score will be assessed by the investigator who has observed the subject
- Updated the definition of 'obvious blood' for subject-reported rectal bleeding within the total, partial, and modified Mayo scores according to Food and Drug

Administration (FDA) interpretation of the FDA Guidance on Clinical Trial Endpoints of Ulcerative Colitis.

- Clarified that the subject will document stool frequency and the rectal bleeding score **daily in the subject diary** and subscores will be calculated as the average of the last 3 non-missing assessments.
- Added histopathology on Day 112, if endoscopy is performed.
- Minor editorial and formatting changes were made.

The following changes were implemented in Protocol Version 5:

- Updated the sponsor's medical contact.
- The name of the organisation Covance was changed to Labcorp.
- Updated that rectally administered 5-aminosalicylic acid that has been stable for <5 weeks is exclusionary.
- Clarified in Section 6 that concomitant medications for ulcerative colitis should be maintained at a stable dose until the last dose of study drug for consistency with the exclusion criteria in Section 4.2.
- Added that over-the-counter and prescription antidiarrhoeals and probiotics are excluded for the duration of the study.
- Added guidelines for performing assessments and procedures during the coronavirus disease-19 pandemic.
- Minor editorial and formatting changes were made.

Abbreviation	Term
AE	Adverse event
ATC	Anatomical Therapeutic Chemical
BID	Twice daily
CI	Confidence interval
CRF	Case report form
ECG	Electrocardiogram
IBDQ	Inflammatory Bowel Disease Questionnaire
ICF	Inform consent form
ITT	Intention-to-treat
MedDRA	Medical Dictionary for Regulatory Activities
MMRM	Mixed Model Repeated Measures
PR	Pulse rate
PT	Preferred term
QD	Once a day
QTcF	Fridericia corrected QT interval
RBS	Rectal Bleeding Score
RR	Respiratory rate
SAE	Serious adverse event
SAP	Statistical analysis plan
SD	Standard deviation
SFS	Stool Frequency Score
SI	International system of units
SOC	System organ class
STEAE	Serious treatment emergent adverse event

CONFIDENTIAL

Page 4 of 30

Statistical Analysis Plan

Sponsor Name: Bridge Biotherapeutics, Inc.

Sponsor Protocol ID: BBT401-UC-005

TEAE	Treatment emergent adverse event
TFLs	Tables, figures and listings
UC	Ulcerative colitis
UCEIS	Ulcerative Colitis Endoscopic Index of Severity
mMCS	Modified Mayo Clinical Score
mESS	Modified Mayo Endoscopic Score

CONFIDENTIAL

Page 5 of 30

Statistical Analysis Plan

Sponsor Name: Bridge Biotherapeutics, Inc.
Sponsor Protocol ID: BBT401-UC-005

1. Source Documents

The Statistical Analysis Plan (SAP) was written based on the following documentation:

Document	Date	Version
Protocol for Korea	02-Aug-2021	5.1 (Korea)
Protocol for other countries	02-Aug-2021	5.0 (Other countries)
[REDACTED]	[REDACTED]	[REDACTED]

2. Protocol Details

2.1 Study Objectives

The primary objective of this study is to explore the efficacy of orally administered BBT-401-1S in inducing a clinical response in subjects with active ulcerative colitis (UC) which is defined as have been diagnosed with active UC for ≥ 3 months prior to Day 1, have an inadequate response or disease relapse despite treatment of UC based on the local standard of care prior to screening, or have a total Mayo score ≥ 6 , and endoscopic subscore ≥ 2 , rectal bleeding subscore ≥ 1 , and a stool frequency subscore ≥ 1 , regardless of standard of care history.

The secondary objectives of the study are:

- to assess the safety and tolerability of orally administered BBT-401-1S
- to explore additional measurements of the efficacy of orally administered BBT-401-1S in inducing endoscopic and clinical remission.

The exploratory objectives of this study are to evaluate the effects of BBT-401-1S on endoscopic response, subject-reported outcomes, histological improvement, biomarkers, and long-term clinical remission.

2.2 Overall Study Design

This study will comprise 2 periods: a randomised, double-blind, placebo-controlled induction phase; and a response-adaptive, double-blind extension phase.

Induction Phase

Subjects will be screened for inclusion in the study within 28 days of Day 1. Eligible subjects will be randomised in a 1:1:1 ratio; 12 subjects will receive 800 mg BBT-401-1S once daily (QD) and placebo QD, 12 subjects will receive 800 mg BBT-401-1S twice daily (BID), and 12 subjects will receive placebo BID. Subjects will receive the first dose of study drug at the study site on Day 1 and will administer study drug away from the study site for 56 days, during which they will attend 2 study site visits on Days 29 and 57. Additionally, subjects will be contacted by telephone on Day 8 for safety and compliance monitoring; however, at the discretion of the investigator, subjects may be requested to attend a study site visit on this day.

CONFIDENTIAL

Page 6 of 30

Statistical Analysis Plan

Sponsor Name: Bridge Biotherapeutics, Inc.
Sponsor Protocol ID: BBT401-UC-005

Subjects who do not agree to participate in the extension phase will attend the study site for a follow-up visit on Day 71.

Extension Phase

Subjects who complete the induction phase will be offered the opportunity to enter the extension phase after the Day 57 visit. Subjects who agree to participate in the extension phase will continue study drug administration while awaiting their clinical remission status from the local reader. Subjects will be assigned to the treatment for the extension phase treatment upon receipt of their clinical remission status.

- Subjects who achieved clinical remission in the induction phase will continue the same treatment.
- Subjects who did not achieve clinical remission in the induction phase and:
 - who received placebo BID will receive 800 mg BBT-401-1S QD and placebo QD
 - who received 800 mg BBT-401-1S QD and placebo QD will receive 800 mg BBT-401-1S BID
 - who received 800 mg BBT-401-1S BID will continue the same treatment.

Subjects will attend the study site on Days 85, 112 (last dose of treatment), and 126 (for Korean sites only). Additionally, subjects will be contacted by telephone on Day 71 for safety and compliance monitoring; however, at the discretion of the investigator, subjects may be requested to attend a study site visit on this day.

The total planned study duration (screening to follow-up) is approximately 20 and 22 weeks for subjects who are enrolled into the extension phase in the sites of Korea and other countries respectively, and approximately 14 weeks for subjects who are not enrolled into the extension phase.

2.3 Sample Size and Power

Approximately 36 subjects will be randomised. There has not been any formal statistical assessment of the sample size. However, the number of subjects is common in early clinical studies and is considered sufficient to achieve the objectives of the study.

3. Efficacy and Safety Variables

3.1 Primary Endpoint(s)

The primary efficacy endpoint is the clinical response rate at Day 57, as measured by a reduction of ≥ 3 points and $\geq 30\%$ improvement from baseline of total Mayo score, which includes a decrease in rectal bleeding subscore of ≥ 1 point or an absolute rectal bleeding subscore ≤ 1 .

Statistical Analysis Plan

Sponsor Name: Bridge Biotherapeutics, Inc.
Sponsor Protocol ID: BBT401-UC-005

The primary safety endpoints are adverse events (AEs) and serious adverse events (SAEs).

3.2 Secondary Endpoints

The secondary efficacy endpoints are:

- Clinical remission at Day 57, as measured by a total Mayo score of ≤ 2 points, with no individual subscore exceeding 1 point
- Achievement of endoscopic remission at Day 57, as measured by a Mayo endoscopic subscore of 0 or 1.
- Change from baseline to Day 57 in the total Mayo score

3.3 Exploratory Endpoints

The exploratory efficacy endpoints are:

- Endoscopic response rate at Day 57, as defined by a ≥ 2 -point reduction from baseline in Ulcerative Colitis Endoscopic Index of Severity (UCEIS) score
- Endoscopic response rate at Day 57, as defined by a reduction of ≥ 1 grade in the Mayo endoscopic subscore
- Modified Mayo remission rate at Day 57, as defined by modified Mayo Clinical Score (mMCS) ≤ 2 , Rectal Bleeding Score (RBS) =0, modified Mayo Endoscopic Score (mESS) ≤ 1 , Stool Frequency Score (SFS) =0 or (1 if at least 1 point drop from baseline)
- Symptomatic remission rate at Day 57, as defined by RBS =0, SFS = 0
- Inflammatory Bowel Disease Questionnaire (IBDQ) total score, as measured by change from baseline
- Histological improvement, as guided by change from baseline in Geboes score
- Biomarkers, including C-reactive protein and faecal calprotectin, as measured by change from baseline
- Clinical remission at Day 112, as measured by a total Mayo score of ≤ 2 points, with no individual subscore exceeding 1 point
- Percentage of subjects with sustained remission at Day 112
- Clinical response rate at Day 112.
- Change from baseline to Day 57 in the partial Mayo score

Statistical Analysis Plan

Sponsor Name: Bridge Biotherapeutics, Inc.
Sponsor Protocol ID: BBT401-UC-005

4. Analysis populations

4.1 Intent-to-treat Population

The intent-to-treat (ITT) population will include all subjects who receive at least 1 dose of study drug, and who have a partial Mayo score recorded on Day 1 and at least 1 post-baseline Mayo score recorded. Subjects are categorized in the treatment group to which they are randomized.

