4.6. Subject Withdrawal

A subject is free to withdraw from the study at any time. In addition, a subject will be withdrawn from dosing if any of the following criteria are met:

- change in compliance with any inclusion/exclusion criterion that is clinically relevant and affects subject safety as determined by the investigator (or designee)
- noncompliance with the study restrictions that might affect subject safety or study assessments/objectives, as considered applicable by the investigator (or designee)
- any clinically relevant sign or symptom (including disease worsening) that, in the opinion of the investigator (or designee), warrants subject withdrawal.

If a subject is withdrawn from dosing, the sponsor will be notified and the date and reason(s) for the withdrawal will be documented in the subject's electronic case report form. If a subject is withdrawn from the study, efforts will be made to perform all early termination assessments, if possible ([Appendix 11](#)). Other procedures may be performed at the investigator's (or designee's) and/or sponsor's discretion. The investigator (or designee) may also request that the subject return for an additional follow-up visit. All withdrawn subjects will be followed until resolution of all their AEs or until the unresolved AEs are judged by the investigator (or designee) to have stabilised.

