5.6. Rescue Therapy

A rescue treatment is defined as any procedure or medication (new medications or medications that have been increased in dose) used for the treatment of new or persistent symptoms of UC.

If a subject who does not exhibit a clinical response experiences worsening of disease (ie, worsening of clinical status or symptoms of UC that require rescue treatment) or disease relapse, study drug must be discontinued, and subjects should be treated as clinically appropriate with conventional treatments for active disease, as determined by the investigator. These subjects should continue in the study for safety assessments but will be considered treatment failures with respect to the intent-to-treat population.

A subject will be considered to have disease relapse when they meet all of the following criteria:

- an increase in UC disease activity after achievement of a clinical response, defined as an increase from nadir or Day 57 in partial Mayo score of ≥ 2 points and an absolute partial Mayo score ≥ 4 points, and
- an endoscopic subscore of ≥ 2 points, and
- exclusion of other causes of increased disease activity that are unrelated to UC (eg, infections or changes in medication).

The date and time of rescue medication administration as well as the name and dosage regimen of the rescue medication must be recorded.

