7.1.3. Mayo Score

The total Mayo score ([Appendix 6](#)) is an instrument designed to measure disease activity of UC, with scores ranging from 0 to 12 points. The total Mayo score consists of 4 subscores, each graded from 0 to 3 with higher scores indicating more severe disease. For the

endoscopic subscore, the modified Mayo endoscopic score will be used to exclude any friability from Grade 1.

- stool frequency (0 to 3)
- rectal bleeding (0 to 3)
- findings on endoscopy (0 to 3)
- physician's global assessment (PGA; 0 to 3).

The total Mayo score (including the findings on endoscopy subscore) measured at screening will be used as the total Mayo baseline score.

The partial Mayo score ([Appendix 7](#)) consists of 3 subscores (stool frequency, rectal bleeding, and PGA).

The modified Mayo score ([Appendix 8](#)) consists of 3 subscores (stool frequency, rectal bleeding, and findings on endoscopy).

Where applicable, the subscores of stool frequency and rectal bleeding will be answered by the subject, subscores of PGA will be assessed by the investigator who has observed the subject, and findings on endoscopy will be assessed by designated reader.

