7.5. Guidelines, Study Assessments, and Procedures During the Coronavirus Disease-19 Pandemic

In view of the coronavirus disease -19 (COVID-19) worldwide pandemic, the safety and wellbeing of study subjects is of primary importance. Study sites must comply with local public health rules.

Although every effort should be made to follow the protocol, subject safety is paramount and the investigator should continue to reassess the risks and benefits of continued study participation for each subject.

If a subject is diagnosed with COVID-19 or is suspected to have COVID-19, they should follow the local treatment and quarantine guidances.

- All diagnoses, procedures, assessments, dosing interruptions, and sequelae should be recorded in the electronic case report form (eCRF).
- Adverse events and SAEs should be reported in accordance with instructions in [Appendix 1](#). If an AE or SAE related to COVID-19 is reported, the investigator should determine whether study drug administration should continue, be interrupted, or stopped.

If a subject is unable to attend study site visits and/or receive study drug, site staff should keep contact with the subject, preferably via telephone calls, to maintain awareness of subject status. If the subject is unable to attend the site, the following options may be considered:

- Subjects may be visited at their home by study staff or other trained professionals (where possible due to social distancing requirements).
- Visits may be performed by telephone or telemedicine to provide continuous medical care and oversight and to identify AEs.

- Blood samples may be collected and analysed at an alternative healthcare facility, at the discretion of the investigator. Although results of these analyses may not necessarily be collected or documented in the study database, it will allow the investigator to assess subject safety.
- If the endoscopy at the end-of-treatment visit can not be performed, the partial Mayo score may be collected by telephone or telemedicine (preferred).

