8.2. Analysis Populations

The **intent-to-treat population** will include all subjects who received at least 1 dose of study drug, have a partial Mayo score recorded on Day 1, and at least 1 post-baseline Mayo score recorded.

The **safety population** will include all subjects who received at least 1 dose of study drug.

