8.4. Efficacy Analyses

8.4.1. Primary and Secondary Efficacy Analysis

All subjects in the intent-to-treat population will be included in the primary and secondary efficacy analyses. Descriptive summaries will be presented for clinical response, clinical remission, and endoscopic remission rates. The estimate and 95% confidence interval (CI) of clinical response, clinical remission, and endoscopic remission rates at Day 57 will be calculated using the exact binomial method for each treatment. The Fisher's exact test will be used to evaluate any differences between treatments.

Missing data will be deemed as "unresponsive". If any event that was not initially anticipated demands to reconsider data handling, then the method of handling the relevant data will be established in the statistical analysis plan.

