5.2 Handling of Dropouts, Missing Data, and Outliers

For the primary and secondary efficacy responder analysis based on the total Mayo score, subjects with missing data will be deemed as "unresponsive". For subjects who received rescue therapy after the first dose of study drug and prior to Day 57, the response status will be deemed as "unresponsive" regardless of the Mayo score value at Day 57.

In terms of the exploratory endpoints, for the endoscopic response rate by total Mayo score, if a subject has no Mayo endoscopic subscore on Day 57, then the last post-baseline measurement prior to Day 57 will be used and the analysis will be based on the imputed value. If a subject does not have any post-baseline Mayo endoscopic subscore measurement, then the subject will be deemed as "unresponsive".

For modified Mayo remission rate at Day 57, if a subject has more than or equal to 2 questions are not answered, then the subject will be considered as "unresponsive". If a subject has only 1 question is not answered, then the last post-baseline question answered prior to Day 57 will be used to calculate the modified Mayo remission rate at Day 57.

For systemic remission rate at Day 57 based by total Mayo score, if a subject has 2 questions are not answered, then the subject will be considered as "unresponsive". If a subject has only 1 question is not answered, then the last post-baseline question answered prior to Day 57 will be used to calculate the systemic remission rate at Day 57.

For the clinical remission at Day 112, the percentage of subjects with sustained remission on Day 112, and the clinical response rate at Day 112 which are all based on the total Mayo score, if a subject has more than or equal to 3 questions are not answered, then the subject will be considered as "unresponsive". If a subject has less than 3 questions are not answered, then the last post-baseline question(s) answered prior to Day 112 will be used to calculate the total Mayo score and information relevant to derive those Day 112 related exploratory endpoints.

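### The set called intent-to-treat is a modified ITT: a dosed subject lost before any post-baseline Mayo score leaves the primary denominator instead of counting as a non-responder

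*SAP*

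**What the plan says.** Both documents put three conditions on the set they call intent-to-treat: at least one dose of study drug, a Day 1 partial Mayo score, and a post-baseline Mayo score. SAP 4.1 admits dosed subjects "who have a partial Mayo score recorded on Day 1 and at least 1 post-baseline Mayo score recorded". Protocol 8.2 requires that they "have a partial Mayo score recorded on Day 1, and at least 1 post-baseline Mayo score recorded". SAP 4.1 adds that subjects are analysed as randomised.

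This set carries the main analyses. Protocol 8.4.1 states: "All subjects in the intent-to-treat population will be included in the primary and secondary efficacy analyses". SAP 6.6.1 names the ITT population for the Fisher comparison at Day 57. SAP 6.1 takes the analysis population as the default denominator for percentages unless a table shell says otherwise.

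The plan also intends failures to count. Under SAP 5.2, in the primary and secondary responder analyses, "subjects with missing data will be deemed as" unresponsive, and Protocol 8.4.1 has the same rule. For subjects who stop study drug because of worsening or relapse, Protocol 5.6 says: "These subjects should continue in the study for safety assessments but will be considered treatment failures with respect to the intent-to-treat population".

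**The concern.** The non-responder rule operates inside the analysis set, and the set is defined partly by what happens after randomisation. Take two dosed subjects who both lack a Day 57 outcome. One has a Day 29 partial Mayo score, is in the set and counts as a failure. The other left before Day 29 without a score and is not counted at all. Nothing in the stated intent of the plan separates these two subjects.

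A Day 57 score is itself a post-baseline score, so the post-baseline condition can remove only subjects with no Day 57 outcome. These are exactly the subjects whom the plan elsewhere treats as non-responders. In any arm with at least one responder, each such exclusion raises the observed rate of clinical response, clinical remission or endoscopic remission. Estimated rates are the main output of a 36-subject exploratory study, so the denominator matters.

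**Working it through.** **Step 1. Who falls out.**

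- Protocol Appendix 11 schedules partial Mayo scores at screening, Day 1, Day 29 and Day 57 in the induction phase. The Day 8 contact, by telephone, has none.
- Diary entries alone do not make a score. Under Protocol 7.1.3 the partial score includes the physician's global assessment, and "subscores of PGA will be assessed by the investigator who has observed the subject". The total and modified scores need endoscopy.
- The early-termination visit would supply a score, but Protocol 4.6 promises only that "efforts will be made to perform all early termination assessments, if possible".

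A dosed subject lost before Day 29 with no Mayo score of any kind is therefore outside the set.

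**Step 2. Whether another analysis restores the subject.** The per-protocol set (SAP 4.4) is a subset of ITT, so it cannot. The sensitivity rules in SAP 6.6.3 are redacted and are not judged here. They could soften the consequence but would not change the primary denominator.

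**Step 3. Inputs for size.** From the documents: three arms of 12 (3 × 12 = 36, the planned total), exact binomial 95% CIs, Fisher's exact test and no multiplicity adjustment. There is no power calculation to reproduce. Assumed, because the documents do not give them: responder counts, number of early losses, a two-sided 0.05 level, and pairwise testing (SAP 6.6.1 does not say whether the test is pairwise or across three arms).

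**Step 4. Rate in one arm.** With r responders and k early losses, the plan as written gives r/(12 − k). Counting the losses as failures gives r/12. The ratio is 12/(12 − k): 1.09 for k = 1 and 1.20 for k = 2.

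| Responders | k = 0 | k = 1 | k = 2 |
|---|---|---|---|
| 4 | 4/12 = 33.3% (9.9 to 65.1) | 4/11 = 36.4% (10.9 to 69.2), +3.0 | 4/10 = 40.0% (12.2 to 73.8), +6.7 |
| 6 | 6/12 = 50.0% (21.1 to 78.9) | 6/11 = 54.5% (23.4 to 83.3), +4.5 | 6/10 = 60.0% (26.2 to 87.8), +10.0 |

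**Step 5. Active arm against placebo.** Each cell gives the difference in percentage points and the pairwise two-sided Fisher p-value.

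| Responders, active v placebo | No exclusion | One active loss | One loss in each arm | One placebo loss |
|---|---|---|---|---|
| 6 v 1 | 41.7; 0.0686 | 46.2; 0.0272 | 45.5; 0.0635 | 40.9; 0.0686 |
| 6 v 2 | 33.3; 0.1930 | 37.9; 0.0894 | 36.4; 0.1827 | 31.8; 0.1930 |
| 6 v 3 | 25.0; 0.4003 | 29.5; 0.2138 | 27.3; 0.3870 | 22.7; 0.4003 |
| 5 v 1 | 33.3; 0.1550 | 37.1; 0.0686 | 36.4; 0.1486 | 32.6; 0.1550 |

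For example, with 6 v 3 and one active loss: 6/11 − 3/12 = 54.5 − 25.0 = 29.5 points.

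**Step 6. How often a test result would change.** There are 66 tables of 12 v 12 with more responders on active than placebo and at least one active non-responder. The p-value newly falls below 0.05 in 8 of them with one active loss, in 1 with one loss in each arm, and in 0 with one placebo loss. These are counts of tables, not probabilities.

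**Step 7. If the test is three-arm.** For 6 v 1 with 2 to 6 responders out of 12 in the third arm, p ranges from 0.0653 to 0.1095 with no exclusion. With one loss in the 6-responder arm it ranges from 0.0341 to 0.0540, and is below 0.05 only when the third arm has 2 or 6 responders.

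**The case against.** The strongest reply is that this is a small matter of naming. The definition is pre-specified, openly stated and the same in both documents. The study is exploratory with no formal sample size. A subject must be dosed, leave before Day 29 and have no score at all, and that may never happen. Several routes keep a subject in: the Day 29 visit, an early-termination visit, and unscheduled visits (Protocol 7). Protocol 7.5 also allows a remote partial Mayo score when the end-of-treatment endoscopy cannot be done. Subjects stopped for worsening should stay for safety assessments and may well be scored. All of this stands. It limits how often the problem would arise, but does not change what happens when it does.

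A second reply is that the 6 v 1 example is favourable to the concern. That is fair: 6 v 3, 6 v 2 and 5 v 1 do not cross 0.05 with one loss, and most tables do not. The case rests on the rate, not on a changed p-value.

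A third is that requiring one dose is also a post-randomisation condition. True, but the first dose is given at the site on Day 1 under double-blind conditions, so it leaves much less room for outcome-related loss than a requirement that may not be met until Day 29.

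Lastly, the table shells and the Korean protocol (5.1), which the SAP lists among its sources, were not available. Either could contain a detail that narrows the gap. SAP 6.6.1 nevertheless names the ITT population for the primary comparison.

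**Conclusion.** The concern holds. The set is a modified ITT under an ITT name, and its post-baseline condition keeps the plan's own non-responder rule from reaching the earliest losses. The two documents agree with each other; the fault is in the shared definition. Within an arm the effect is upward whenever there is a responder: 3.0 to 4.5 points for one loss and 6.7 to 10.0 for two, assuming 4 to 6 responders among 12. Between arms the direction depends on where the losses fall, and a changed test result generally needs losses concentrated in the active arm. The reading of the text is firm. The sizes rest on assumed responder counts and losses, and the test results also on an assumed 0.05 level and, apart from Step 7, pairwise testing. The point should be corrected because it is cheap, although the gap is narrow.

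**What to change.** Define the primary efficacy set in SAP 4.1 and Protocol 8.2 as all randomised subjects who received at least one dose, analysed as randomised, with no Mayo-score condition. State that a subject without a Day 57 outcome counts as a non-responder for clinical response, clinical remission and endoscopic remission. Keep the present set as a sensitivity analysis named modified ITT.

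The Day 1 partial Mayo condition can go too, because the total Mayo baseline is the screening value (Protocol 7.1.3, SAP 5). Dropping it may bring back subjects who do have a Day 57 outcome, including responders, so that part of the change could move a rate either way.

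The SAP should also say which set serves the ANCOVA of change in total Mayo score, to which non-responder counting does not apply, and which serves the exploratory and baseline tables now tied to ITT.

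The cost is wording in the SAP and the protocol, with the Korean version aligned. No extra data are needed, and SAP 4.2 already uses the dosed-only condition for safety. If early losses occur, reported rates will be lower than under the present definition by the amounts in Step 4.
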